## Abstract

**Project Background:** Women Veterans are the fastest growing segment of Veterans Health Administration (VHA) users. This dramatic growth has created challenges for VHA. Rates of depression, anxiety, and mental health comorbidity are disproportionately high among women Veterans. Furthermore, a high rate of women Veterans' attrition from VA care, along with organizational barriers to care, substantiate that organizational changes are needed in order to engage and retain women Veteran VHA users in evidence-based, patient-centered care.

**Project Objectives:** The **Enhancing Mental and Physical health of Women through Engagement and Retention (EMPOWER) QUERI** addresses VHA Blueprint for Excellence Strategy 6, by advancing "personalized, proactive, patient-centered" care models, and Transformational Strategy 7.2.g by implementation of innovative care models in women Veterans' health care." The EMPOWER QUERI Program is designed to improve women Veterans' engagement and retention in evidence-based care for mental health. To achieve this impact goal, we propose a cohesive portfolio of projects with the following aims: (1) To use an evidence-based implementation strategy that emphasizes local tailoring of care models, multilevel stakeholder engagement, and systematic evaluation of complex implementation processes in order to enrich organizational capacity for innovations in women Veterans' VHA health care; (2) To implement personalized, proactive, patient-centered innovations in VHA women's health that are acceptable, feasible, satisfactory, relevant, and effective for both providers and patients, thereby encouraging women Veterans' engagement and retention *and* sustainability of the innovations; and, (3) To generate implementation "playbooks" for our partners that are scalable and serve as guidance for future implementation of a broader array of evidence-based women's health programs and policy.

**Project Methods:** "Implementation of Tailored Collaborative Care for Women Veterans" will evaluate implementation of an evidence-based collaborative care model tailored to enhance provider- and system-level capabilities to address women Veterans' anxiety and depression treatment needs, thereby improving organizational primary care-mental health integration (PC-MHI) effectiveness and women Veterans' engagement and retention in PC-MHI. The study will use a modified stepped wedge design and will apply the evidence-based Replicating Effective Programs (REP) implementation strategy. Mixed methods implementation evaluations will focus on investigating primary implementation outcomes of adoption, acceptability, feasibility, and reach. Multilevel stakeholder engagement will be prioritized. Program-wide organizational-, provider-, and patient-level measures and tools will be utilized to enhance synergy, productivity, and impact. As a coherent program of women's health implementation research and quality improvement, the proposed EMPOWER QUERI will constitute a major milestone in achieving BPE strategies and realizing women Veterans' engagement and, ultimately, empowerment in our VHA system.

## List of Abbreviations

1. EMPOWER.....Enhancing Mental and Physical health of Women through Engagement and Retention
2. PCMHI.....Primary Care-Mental Health Integration
3. PCP.....Primary Care Provider
4. MH.....Mental Health
5. CCWV.....Collaborative Care for Women Veterans
6. WATCH.....Women's Assessment Tool for Comprehensive Health
7. CALM.....Coordinated Anxiety Learning and Management
8. PACT.....VA's Patient-Aligned Care Teams
9. WH.....Women's Health
10. WHS.....Women's Health Services
11. GLA.....Greater Los Angeles
12. NCP.....National Center for Disease Prevention and Health Promotion
13. BPE.....Blueprint for Excellence
14. EMR.....Electronic Medical Record
15. REP.....Replicating Effective Programs
16. TECH.....Tool for Evaluating Research Implementation Challenges
17. WHRN.....Women's Health Research Network
18. PBRN.....Practice-Based Research Network
19. DART.....Data Access Request Tracker

**Protocol Title:**

**IMPLEMENTATION OF TAILORED COLLABORATIVE CARE FOR WOMEN VETERANS (CCWV)**

***NOTE: Component A (approved 12/27/2016) involves Key Stakeholder VA Staff Participants, and will be coordinated by the PI at Greater Los Angeles VA Healthcare System. Component B involves Patient Human Subjects and additional sites outside of Greater Los Angeles VA.***

# Introduction

## BACKGROUND

Almost half (48%) of women Veterans have at least one mental health (MH) condition, with depression as the most common MH condition among women Veteran VA users (24% in FY14), followed by PTSD (14%) and anxiety (8%). Depression and anxiety are substantially more prevalent among women Veterans than men. Women Veterans are also more likely than men to have comorbid MH conditions, and they are more likely to have experienced military sexual trauma (MST) and intimate partner violence (IPV) Like their male counterparts, women Veterans tend to have complex mental health needs. However, in contrast with men, a significant proportion of women's symptoms, losses, and treatment contraindications may be related to reproductive phases and experiences, gendered trauma histories, and gender role responsibilities.

Women Veterans' distinctive MH needs challenge the organization to appropriately connect women to MH providers who understand their unique vulnerabilities, and to support their navigation of often fragmented MH care options offered across VA primary care (PC) and MH settings. Depending on the VA site, women may have access to integrated MH care in general PC clinics, in a separate portion of a general PC clinic set aside for women, or in stand-alone women-only clinics, with variable access to women-only care options and same-gender providers when preferred. MH clinics may have no special arrangements for women, or may have some providers to whom women are preferentially assigned. At a few sites, women-only MH clinics may be available, or if the site has a comprehensive women's PC clinic, full-service specialty MH care may be co-located. Such highly variable models of MH care delivery in PC and MH further challenge the system to engage women in services in a timely manner, and to support their retention in care.

Collaborative care models have a strong evidence base for enhancing patient engagement and retention in PC-based MH care for depression, and the VA has extended application of collaborative care to many other mild to moderate conditions, including anxiety disorders and alcohol misuse. The VA's approach to integrated MH involves collaborative care with two components: co-located MH professionals who are integral components of the PC team, and MH care management. While co-location has been achieved at many sites, implementation of care management has been limited, especially in women's clinics. The VA endorses three collaborative care models that emphasize different elements of care management: Behavioral Health Lab, White River Junction, and Translating Initiatives in Depression into Effective Solution (TIDES). A recent report on Integrating Mental Health into VA's Patient-Aligned Care Teams (PACT) suggests that further work should be directed at understanding the advantages and disadvantages of each approach, and suggests moving away from branded approaches, toward blended models with local tailoring.

VA policy specifies that MH services must be provided in a manner that recognizes that gender-specific issues can be important components of care. With attention to gender-specific

concerns, collaborative care is a promising model to improve PC-MH integration for women Veterans. We propose implementation of tailored “Collaborative Care for Women Veterans” (CCWV) that encourages local blending of elements from VA-approved models with a PC-friendly evidence-based, computer-assisted cognitive behavioral treatment (CBT) platform for anxiety and depression.

## RATIONALE

The rationale for this project is based on five fundamental premises: 1) PC and MH care for women Veterans are complex and diverse (as described above); 2) anxiety and depression among women Veterans can and should be treated in PC; 3) improvements are needed in PC-MHI for women in these complex care structures and settings; 4) collaborative care *designed for women Veterans* would benefit the VA, providers, and women Veterans themselves; and 5) blended models of existing collaborative care models or components, with some enhancements, are needed in order to fit with local WH structures, needs, and resources.

Anxiety and depression among women Veterans can and should be treated in the PC context. Since 2007, Primary Care-Mental Health Integration (PC-MHI) in VHA has evolved into a requirement at all VHA medical centers and large community-based outpatient clinics. VA WH policy now requires that basic mental health services be provided in the same physical location as women's primary care, whether in a gender-neutral primary care clinic, in shared separate space in the gender-neutral clinic, or in a separate WH center. In addition, WH clinics must have co-located MH and social work services. Assessment and psychosocial treatment need to be available in women's PC for MH disorders, including depression and problem drinking, within the parameters of PC-MHI.

Improvements are needed in PC-MHI for women in VA's complex WH care structures and settings. Women's Assessment Tool for Comprehensive Health (WATCH) data provided to us by our WHS primary partners indicates that roughly 63% of VA healthcare settings (including medical centers and community-based outpatient clinics) have availability of PC-MHI such that a woman can “see a PC-MHI provider when clinically indicated...whenever this clinic is open to see patients on a timely, same-day basis.” Unpublished interview data from several of our team's qualitative key informant studies suggest that MH services available in women's PC (or in an adjacent women's MH clinic) tend to be longer-term specialty MH services (as opposed to PC-MHI assessments and brief therapies) as well as women-only treatment groups, particularly for MH problems associated with MST experience. Informants have tended to report good communication between PC and MH providers, with “warm hand-offs” and curb-siding easily occurring in the clinic, but without a care management component to assess and triage the more and less severe cases to appropriate services.

True integration of MH supports for PC-based management of mild to moderate MH conditions may be overshadowed by co-located specialty MH services for more serious conditions. On the

other hand, when women receive their PC in mixed-gender general PC clinics, women's proportional minority creates challenges to provision of integrated services that can provide choice of women-only and same-gender provider services when desired, and may limit access to integrated MH providers experienced in working with the unique trauma experiences of women in the military. Varying care arrangements and varying needs for gender-specific choices make the “glue” of a care management process very important to help women Veterans access appropriate services, while also making care management more difficult to implement.

Furthermore, work from the VA Women's PBRN indicates that depression and PTSD are associated with women's strong preferences for designated women's mental health services, as well as treatment within the PC setting. According to a recent national survey of women Veterans, access to MH care for these conditions is good, but nearly half of respondents reported that VA MH services do not fully meet their needs. Our WH, MH, and PC partners have urged us to use this QUERI implementation research opportunity to improve PC- MHI for women Veterans with depression and anxiety.

Collaborative care designed for women Veterans with depression and anxiety would benefit the VA, providers, and women Veterans themselves. Numerous similar models of collaborative care have been tested, primarily for care of depression in primary care settings, both outside the VA, and in military and VA populations. A 2006 meta-analysis found that collaborative care is more effective than standard care in improving depression outcomes in the short and longer terms, and concluded that future research needs to address the implementation of collaborative care.

The overall higher MH burden among women Veterans, and greater complexity of presentations, adds to the challenges of tailoring care management to meet women's needs. Models based on treating one MH condition, such as depression, tend to exclude patients with more complex issues. Our recent work has found that over one-quarter (27%) of women Veteran VA users have two or more MH conditions. Though depression is the most common MH diagnosis among women Veterans, depression very often presents together with anxiety disorders; in fact, depression-plus-anxiety and depression-plus-PTSD are tied for the two most prevalent co- occurring MH conditions among women Veterans. Therefore, collaborative care management models that incorporate PC-friendly transdiagnostic brief treatment options for co-morbid presentations may be particularly suited to women Veteran populations. In addition, for those women whose MH needs exceed what can be offered in PC, strategies to support engagement in specialty care (especially when women-only settings are not available), as well as strong stepped care and referral management components will be important.

Because of the need for transdiagnostic and flexible models to meet women's MH needs, we propose to enhance existing VA models with elements of another collaborative care management model, Coordinated Anxiety Learning and Management, or CALM. CALM is a flexible, patient preference-driven model for multiple anxiety disorders (panic, generalized anxiety, social anxiety, PTSD) and depression in PC. Evidence for the effectiveness of CALM

comes from a large (n = 1004) randomized controlled effectiveness trial, in 17 US primary care clinics with 71% women. Women receiving collaborative care showed larger reductions in anxiety, greater improvements in mental health functioning, and larger reductions in days of restricted activity than women receiving usual care, while men showed no differences in these measures. Women receiving the computer-assisted CBT (which used disorder-specific treatment modules) attended more sessions of psychotherapy, completed more modules of therapy, expressed more commitment, and viewed psychotherapy as more helpful than did men. Although Veterans were not the focus of the CALM trial, past trials using cognitive behavioral strategies for anxiety and depression in VA PC clinics have demonstrated the value of the general approach. Importantly, the effectiveness of CALM was strongly related to level of engagement; outcome was predicted by completing exposures and homework and attending more frequently. CALM's care management components closely mirror those emphasized in VA-approved models described above, including screening and initial assessments using structured instruments; regular monitoring of treatment adherence and side effects using a standardized protocol; patient education and activation; decision support using a protocol to determine patient preference for medication vs a brief computer-assisted CBT-based therapy or both; a stepped care protocol supported by regular brief assessments and a patient tracking system; and assistance with referral to specialty care when appropriate. Our ability to incorporate elements of CALM for CCWV is strengthened by many key factors: 1) the CCWV Co-PI, [name], was involved in the original CALM trial and is an expert on the CBT platform; 2) one of the main CALM developers, [name], has guided our study design and is a member of our Strategic Advisory Group; 3) CALM is currently being evaluated in a VA HSR&D CREATE hybrid type III implementation study, and the research team has agreed to share with us their VA-tailored version of the web-based CBT platform as well as their implementation results; 4) the lead of the CALM implementation evaluation, [name], is a nationally recognized implementation scientist and will also serve on our Strategic Advisory Group; and 5) one of our key partners, the PC-MHI National Medical Director, [name], strongly endorses our incorporation of CALM, indicating in his letter that this project will take existing PC-MHI programs "to a new level."

## 2.0 Objectives

### SPECIFIC AIMS

Our specific aims are to:

1. In four PBRN sites, blend and tailor existing primary care-based collaborative care models with an evidence-based CBT platform to provide evidence-based, patient-centered collaborative care for women Veterans (CCWV) with anxiety and/or depression;
2. Implement the tailored CCWV in the four PBRN sites; and

3. Evaluate CCWV implementation using a modified stepped wedge design and conduct an implementation-focused evaluation to further refine CCWV to facilitate future spread.

Achieving these aims will help achieve VA comprehensive PC policies for women Veterans and VA MH Strategic Analytics for Improvement and Learning (SAIL) performance goals of population coverage, continuity of care, and experience of care.

Our secondary aims focus on factors that empower Women Veterans to engage in and benefit from collaborative care. Specifically, we will evaluate a) effects of patient activation and engagement with care on retention in and experiences of CCWV, and b) changes in MH symptoms, patient activation, health-related quality of life, and care experiences as a function of participation in CCWV. We hypothesize that a) more highly activated women and women with greater increases in activation will demonstrate better retention in care and report better care experiences, and b) symptoms, patient activation and quality of life will improve as a function of CCWV participation.

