### REP Implementation Phases

**Pre-conditions (Aim 1):** The need for CCWV has been established and the review of effective interventions has been conducted (see above). To ensure that the care model fits local settings and stakeholder priorities, the PI and Co-Investigator [name] will visit the sites and meet with the local team to discuss local structures, care models and processes, educational needs, as well as elements of the proposed CCWV and tailoring options that we have conceptualized (Table 3). Using the TECH, the local team will discuss options for CCWV implementation and anticipated barriers to implementation. Also during this phase, interviews and surveys will be conducted with all consenting key stakeholders, with the exception of patients who will be interviewed and surveyed in the implementation phase (see below).

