Disorder, depression). CCWV is an innovative care model that is proactive, patient-centered and personalized to each woman that has an appointment with the care manager. Specifically, the care manager assists the patient in deciding which type of treatment she wants to pursue (CBT, medication, or both). During or shortly after the initial meeting with the care manager, each woman will be asked by the RA if she is willing to participate in our research project, meaning that she will be asked to complete a brief written battery of measures (§3.3.3.3) and a short qualitative interview at baseline (after the first or second visit with the care manager) and at six-months post-baseline. Women who enroll after the baseline window will not be eligible for baseline survey measures; however they can participate in interviews. Participants who enroll in research after the baseline period, and any women who are otherwise unable or unwilling to complete the written surveys, will be invited to consent to participate in other components of the research (i.e., qualitative interviews, , data obtained from medical record).

For women who choose CBT, the CALM-trained provider will then meet with the patient weekly to review the CALM CBT modules. The program includes five general modules (introduction, psychoeducation, self- monitoring, breathing retraining and relapse prevention), and three other modules that are customized to each anxiety disorder (cognitive restructuring, in vivo exposure and interoceptive exposure), which are tailored to each anxiety disorder. Depression modules are also available. The CALM CBT platform is a computer-assisted delivery system. The provider sits with the patient in front of the computer and directs the individual to review the appropriate material, clarifying and individually tailoring. The program contains educational material as well as skills training and exposure exercises. The entire program is typically completed within eight 60-minutes sessions.

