### ***Veteran Involvement and Characteristics***

This 4-site project aims to inform the VA regarding implementation of collaborative care for women Veterans (CCWV). The study is primarily focused on implementation outcomes such as adoption, acceptability, feasibility, satisfaction, and reach, as well as patient engagement and retention; patient clinical outcomes (symptoms, etc.) though examined, are secondary. After IRB approval, at each participating site, we will enroll approximately 130 women Veterans who are referred by their primary care provider (PCP) or another referring provider to the CCWV care manager. Any woman referred to the care manager (and therefore initially screening positive for anxiety, depression, and/or PTSD) is eligible to participate. We will stop consenting enrollees once we have reached up to 80 women who have had an encounter with the care manager and who consent participate in the research, in order to complete data collection with 65 women at each site. Our goal is to have 260 women total (across the 4 sites) engaged in care management over the course of the study. Participation in CCWV consists of completion of the surveys, interviews, and access to relevant medical record data.

**Routine Clinical Care versus Research.** Meeting with the care manager and participating in Coordinated Anxiety Learning and Management (CALM), being followed by the care manager for medication adherence, psychiatric treatment and medication, or other mental health treatments are routine clinical care available to any woman Veteran seen at a participating primary care or women's health clinic. Consenting to research involves completing the research surveys, research interviews, and granting permission to access selected medical record data as part of an evaluation of the implementation outcomes and secondary clinical outcomes described above. Participants who enroll in research after the baseline period, and any women who are otherwise unable or unwilling to complete the written surveys, will be invited to consent to participate in other components of the research (i.e., qualitative interviews, data obtained from medical record). Patients do not have to consent to participating in research in order to receive routine clinical care with the care manager.

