### **Patients**

Inclusion Criteria: female VA patients who are referred to the care manager for further mental health assessment and/or care.

Exclusion criteria: Non-VA patients; less than 18 years of age; anyone who is unable to provide consent.

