In the pre-conditions transcripts, we will identify clinic organization, provider and staff roles, existing care arrangements for women Veterans, and perceived acceptability and feasibility of the CCWV program. We will synthesize this information with patient survey data to create baseline summaries of care as usual, and to tailor our marketing and implementation strategies for use at the sites. In mid-implementation interview data, we will identify factors facilitating and impeding implementation of the care model, and strengths and weaknesses of the model as implemented. We will assess the extent to which components of the model are being implemented, and which components are efficient and easy to incorporate into routine care. We will explore whether particular components appear to be of limited value in improving care and examine clinic and provider characteristics associated with varying levels of care model implementation and effectiveness. In post-implementation interview data, we will take a summative approach to characterizing overall experiences of and perspectives on implementation, with a particular focus on recommendations for scale up and spread.

For providers, we will track changes in perceptions about the utility and impact of CCWV on clinical practice from pre-conditions to maintenance. We will also be interested in the experiences of the care managers and other stakeholders with regard to working specifically with women, eliciting their preferences, providing the CBT, and coordinating with MH providers. For patients, we will compare and contrast data from those who selected different treatment options. In order to evaluate the patient impact of CCWV, we will assess changes in patient perceptions of their MH symptoms, self-efficacy, activation, health-related quality of life and functioning. We will also collect information on demographics, trauma history, health care, mental health care, and experiences of care.

**Quantitative Analysis:** We will use the modified stepped wedge design to evaluate the implementation across the providers at four sites. CCWV will be defined as “turning on” when a provider refers a patient to the CCWV care manager. We will model the effect of CCWV implementation on referral rates, while controlling for organizational level, provider level and patient level covariates.

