In addition to project key personnel, the overall EMPOWER QUERI Implementation Core will be involved in data analysis. The Implementation Core is directed by [name] (EMPOWER QUERI PI), an experienced and highly trained implementation scientist. She will be supported by a seasoned team of Co-Investigators, many of whom also have implementation research experience. Drs. [name] and [name] will lead the qualitative analysis. The implementation core personnel are supported by several internationally recognized implementation scientists on the Scientific Advisory Group, including Drs. [name], [name], and [name].

Impact-focused evaluation: Secondary aims for the project focus on factors that empower Women Veterans to engage in and benefit from care. We will use generalized linear mixed models (GLM) to evaluate a) cross-sectional relationships of patient activation, health-related quality of life, and care experiences at enrollment, with provider and site characteristics, adjusting for patient social and demographic characteristics; and b) prospective changes in patient activation, health-related quality of life, and care experiences from enrollment to 6-month follow-up, adjusting for patient, provider, and site characteristics. We will also construct multi-level mediation and moderation models to explore whether engagement-related factors such as patient activation, strength of treatment preferences, or the communication subscale of the CAHPS are associated with greater benefit from or satisfaction with care.

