### Access, Storage and Handling of Secondary Data

In addition to surveys and interviews, other outcome data will be extracted from national VA data systems, and patient medical record charts. Data from VA electronic data systems will initially include patients' social security numbers (SSN) along with any other identifiers, since these are used to assure that the data matches the project participants. We will merge the extracted data with our existing research data. Once the data have been checked to ensure the merge has been successful, within the shortest possible time period, the SSNs will be removed from the analytic data file and stored in a link file kept in a separate, high security folder on secure VA server. Each subject will already have been assigned a project ID number that does not contain any identifiers. The subject's ID number will replace the SSN in the files. All information linking subject identifiers to their data will be destroyed in accordance with the VA Records Control Schedule and guidance from the CIRB.

VA records data will be obtained from CPRS, DSS or CDW. In order to obtain data, the project team will work with a list of SSNs of patients consented and enrolled in the study. Project or VA-certified database analysts will be given this list of SSNs and will then run a query to extract the needed data, either working in the VINCI platform or downloading the data to a temporary folder on the CSHIIP

secure server. Extracted data will be placed into our secure folder on the local CSHIIP server and coded for analysis. This data will always remain behind the VA firewall.

All the above data are stored and backed up on a secure VA server. Computer users “lock” their workstations when not actively in use and office doors are locked when staff members are not present. Hard copies of sensitive data are stored in a separate locked filing cabinet in a locked office.

Special consideration and precautions will be taken with regard to sharing information provided by individual employees with supervisors and co-workers. While general information derived from employee interviews related to relevant clinical practices, resources, quality improvement activities, and barriers/facilitators will be shared with other site participants in aggregate or synthesized form, detailed information that would allow identification of individual employee responses will not be shared with supervisors of the employees or their co-workers.

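### Secondary hypothesis (b) attributes patient improvement to CCWV participation, but the planned analysis is uncontrolled pre-post change among participants only

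*Combined protocol and SAP*

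**What the plan says.** Section 2.0 (Specific Aims) sets secondary aim (b) as changes that depend on taking part in CCWV, and predicts that "symptoms, patient activation and quality of life will improve as a function of CCWV participation".

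The analysis that answers it is in section 5.6 (Impact-focused evaluation). It is a generalized linear mixed model of "prospective changes in patient activation, health-related quality of life, and care experiences from enrollment to 6-month follow-up", adjusted for patient, provider and site characteristics. Symptoms are in the hypothesis but not in this list.

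On entry, Veteran Involvement and Characteristics states: "Any woman referred to the care manager (and therefore initially screening positive for anxiety, depression, and/or PTSD) is eligible to participate". The formal criterion in section 5.4 is looser and sets no score threshold: "female VA patients who are referred to the care manager for further mental health assessment and/or care".

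The research measures are taken "at baseline (after the first or second visit with the care manager) and at six-months post-baseline" (section 5.1, Procedures under Implementation). The same part of the plan classes clinical outcomes as secondary to the implementation outcomes.

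**The concern.** A hypothesis about improvement as a function of participation needs a contrast: participants against non-participants, or more participation against less. The named model has neither. A mean change in one exposed group combines any CCWV effect with regression to the mean, natural recovery, secular trend, other care received over six months, and differences between women who complete follow-up and those who do not. Adjusting for patient, provider and site characteristics does not separate these, because every surveyed woman shares the same exposure and the same route into the study.

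If the change is significant, the hypothesis as worded would be declared supported when the data cannot distinguish it from these alternatives. The plan mentions neither regression to the mean nor natural recovery.

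**Working it through.** **Step 1. Is there a comparison anywhere in the plan for these outcomes?**

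- *Surveys.* Section 5.1 says data collection occurs in every REP phase, but the REP Implementation Phases text excludes patients from the earlier ones: "with the exception of patients who will be interviewed and surveyed in the implementation phase". There are therefore no patient surveys from control periods.
- *Records.* Extraction starts from a "list of SSNs of patients consented and enrolled in the study", so unexposed women are not in the records data either.
- *Stepped wedge.* Its stated outcome is different: "We will model the effect of CCWV implementation on referral rates". The power analysis likewise uses a binary referred/retained outcome.
- *Exposure.* Section 5.6 names activation, strength of treatment preference and CAHPS communication as engagement-related factors. Amount of participation is not named, although CCWV utilization and CALM modules are collected (section 5.5).

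So there is no unexposed group and no named dose variable.

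**Step 2. What could selection alone produce?**

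The plan gives no sample-size figure for pre-post change. Its 8.78 providers per site concerns the binary outcome, and it cannot be rebuilt because no pair of target proportions is stated.

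Inputs from the plan: n = 4 × 65 = 260 women with complete data (section 5.2), and alpha 0.05. Sidedness is not stated; I take it as two-sided, so chance alone gives improvement 2.5% of the time.

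Assumptions: normal scores; a paired test standing in for the mixed model; clustering ignored unless stated; and a screen-positive share p of 24% or 48%. Those shares are the Background's prevalences of depression and of any mental health condition, used as stand-ins. All correlations are assumed.

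Mean screen score among the selected women, in SD: λ = φ(z_p)/p = 1.295 at 24% and 0.830 at 48%.

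*Case A: the baseline is the selecting measure.* Shift = (1 − r)λ; SD of change = √(2(1 − r)); probability = Φ(shift × √260 / SD − 1.96). For p = 48% and r = 0.9: shift = 0.1 × 0.830 = 0.083; SD = 0.447; 0.083 × 16.12 / 0.447 = 2.99; Φ(1.03) = 0.85.

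| r | Shift (probability), p = 24% | Shift (probability), p = 48% |
|---|---|---|
| 0.5 | 0.65 (1.00) | 0.42 (1.00) |
| 0.7 | 0.39 (1.00) | 0.25 (1.00) |
| 0.9 | 0.13 (1.00) | 0.08 (0.85) |

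A design effect of 2 leaves an effective n of 260/2 = 130. The smallest probability, 0.85, then falls to 0.56; the other r = 0.9 cell falls to 0.91, and the r = 0.5 and 0.7 cells stay at 0.96 or above.

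*Case B: the baseline is separate from, and later than, the screen.* Shift = (correlation of screen with baseline − correlation of screen with six months) × λ. For example, (0.8 − 0.6) × 1.295 = 0.26. Probabilities are from 2,000 simulated trials per row, with baseline to six-month correlations of 0.60, 0.65, 0.70, 0.70 and 0.70 down the table.

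| Correlation with screen, baseline to six months | p = 24% | p = 48% |
|---|---|---|
| 0.80 to 0.50 | 0.39 (1.00) | 0.25 (1.00) |
| 0.80 to 0.60 | 0.26 (1.00) | 0.17 (0.91) |
| 0.75 to 0.65 | 0.13 (0.75) | 0.08 (0.41) |
| 0.70 to 0.65 | 0.07 (0.26) | 0.04 (0.13) |
| 0.70 to 0.70 | 0.00 (0.02) | 0.00 (0.02) |

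*Case C: activation or quality of life.* Women are not selected on these directly, so the screen correlations are multiplied by an assumed cross-correlation. At 0.3, with the 0.8 to 0.6 fall: 0.3 × 0.2 × 1.295 = 0.08 SD. Across the 0.80 to 0.60 and 0.75 to 0.65 falls, cross-correlations of 0.2 to 0.3 give 0.02 to 0.08 SD and probabilities of 0.05 to 0.32. A cross-correlation of 0.5 gives 0.14 to 0.70.

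**Step 3. Completion.** Up to 80 women per site consent so that 65 complete: 15/80 = 18.75% loss. If completion is related to improvement, it adds a further bias that the model does not address.

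**The case against.** A reader might infer that regression to the mean by itself would confirm the hypothesis whether or not CCWV works. The documents do not support that. The research baseline follows the first or second care-manager visit, so some regression may already have happened. Section 5.4 sets no score threshold, and referral covers women with possible disorders. Activation and quality of life are not selection variables. The argument is strongest for symptoms, the outcome for which section 5.6 names no model. All of this stands, and it is why the result is a range. It is limited for symptoms, however: those scores are the care manager's own measures taken from the record (section 5.5), and Table 3 has the care manager assess women at the start and offer treatment to those who are positive. If that score serves as baseline, Case A is the nearer one.

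A reader might also say that nothing in the plan relates outcome to participation. That is too strong. Section 5.6 plans mediation and moderation models for engagement-related factors and a qualitative comparison by treatment chosen, and the power analysis assumes that longer retention goes with better outcomes. What is missing is amount of participation as a named predictor of change.

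Finally, a reader might expect pre-post change to appear in the implementation playbook as proof of benefit. No passage says so. The playbooks are fed by implementation outcomes, and the evidence for CALM is taken from an earlier randomized trial. The secondary status of the clinical outcomes lowers the stakes, but it does not make the causal wording testable.

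**Conclusion.** The point holds as a mismatch between hypothesis and analysis. Followed as written, section 5.6 can describe change among participants but cannot show that it is a function of participation. This conclusion rests on the documents alone and needs no assumed correlation.

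How far selection could mislead is uncertain. With no CCWV effect, the chance of a significant symptom improvement spans about 0.02 to near 1.00, depending on how close the baseline is to the screen and how quickly correlation with the screen falls. The selected shares and correlations behind that range are assumptions, and clustering would lower the higher figures somewhat. For activation and quality of life the mechanism is weaker, though secular trend, other care and selective completion remain uncontrolled. Because the outcomes are secondary, this should be corrected but does not threaten the implementation evaluation.

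**What to change.** 1. In section 2.0, reword secondary aim (b) and its hypothesis as change during CCWV, without causal wording.
2. In section 5.6, add symptoms to the change models and name the measure and the baseline time point.
3. Add graded exposure (CCWV utilization or care-manager contacts, and CALM modules) as a predictor, adjusted for baseline severity. Report it as associational only, because retention is self-selected and this term cannot rescue an effect claim.
4. State that no conclusion on CCWV's clinical effect will be drawn from pre-post change.

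The cost is a more modest claim and slightly more analysis; no new data collection is needed.

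Keeping an effect claim would be a larger step. It would need the same measures from women selected in the same way before implementation. As an illustration, detecting an assumed 0.3 SD difference takes 175 women per group at 80% power (393 at 0.2 SD, 63 at 0.5 SD), before any allowance for clustering.
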